We will randomize patients with confirmed COVID19 with acute hypoxic respiratory failure (1. O₂ saturation below 93% on minimal 2l/min O₂ therapy; and/or 2. PaO₂/FiO₂ below 350 mmHg) to receive up to 14 days of SC Zilucoplan® on top of standard of care (active group A), or to receive standard of care treatment (control group B). Randomization will be done at a 2:1 ratio active: control group. In the active group A, patients will additionally receive daily antibiotics (daily 3rd generation cephalosporin IV while in hospital, followed by oral ciprofloxacin while discharged) as primary prophylaxis against meningococcal disease until 14 days after the last dose of Zilucoplan®. Control group B will receive standard of care and prophylactic antibiotics (3rd generation cephalosporin IV) for only 1 week (or until hospital discharge whichever comes first), to control for the effects of antibiotics on the clinical course of COVID-19. In case of allergies to these antibiotics, or on clinical indication, these antibiotics may be switched to antibiotics that also cover *Neisseria meningitidis*.

To measure the effectiveness of Zilucoplan® on restoring lung homeostasis, the **primary endpoint** of this intervention is **measuring change in oxygenation parameters** comparing baseline values (pretreatment) to values predose day 6 and to values at day 15 (or discharge whichever comes first) post-randomization in group A and group B and the differences in these values between group A and group B.

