Considering the acuteness of the indication and short duration of treatment (maximum of 14 days inhibition of C5 with Zilucoplan[®], followed by a post-dosing inhibition of C5 for a maximum of 14 days) in the hospital, vaccination and induction of humoral immunity prior to initiation of Zilucoplan[®] therapy is not feasible in the context of COVID-19 with hypoxia. Vaccination during the period of COVID-19 with high fever and complement activation, is also not a safe option. Therefore, the risk of neisserial infection must be mitigated by concomitant administration of appropriate antibiotics (e.g. 3rd generation cephalosporin IV, ciprofloxacin PO) from the beginning of Zilucoplan[®] administration until 14 days after cessation of Zilucoplan[®]. In the hospital setting this will be achieved by daily IV administration of ceftriaxone (or cefotaxime). As soon as the patient is discharged, oral daily ciprofloxacin will be given until at least 14 days after the last dose of Zilucoplan[®]. To correct for the effects of antibiotics on the course of COVID-19 disease, the control group B will receive 1 week (or until hospital discharge whichever comes first) of IV ceftriaxone (or cefotaxime) during the hospital stay. In the control group, oral ciprofloxacin post ceftriaxone or cefotaxime is not required. In case of allergies to these antibiotics, or on clinical indication, these antibiotics may be switched to antibiotics that also cover *Neisseria meningitidis*.

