should continue prophylactic antibiotics once daily for 14 days after the last dose of Zilucoplan®. If the participant is discharged before D28, daily prophylactic antibiotic treatment will be taken orally until 14 days after last dose of Zilucoplan®. For Arm B, the 28-day assessment period comprises SOC treatment up to 28 days post randomization or hospital discharge, when the D28 nominal day procedures. Arm B will only have 1 week of IV prophylactic antibiotics once daily, starting on D1. If hospital discharge occurs before D28 post-randomisation, both SOC and antibiotic treatment will cease and the D28 nominal day procedures will occur by telephone.

For both arms, whilst in hospital, assessments will continue on a daily basis as possible, until discharge or Day 28 is reached. If discharge is prior to D28, no daily assessments will be carried out – just the D28 telephone call.

The maximum time window for an eligible participant signing the informed consent document (and starting screening) and being randomised is 24 hours. It is assumed that first dose occurs very soon after randomisation.

An interim analysis (Interim 1) of the primary endpoints is planned after approximately half the planned number of participants have been dosed and had the opportunity to complete D15 assessments. The purpose of the interim analysis is to understand if there is already enough evidence to prompt further work on COVID-19 treatment with Zilucoplan®. There is currently no plan to stop the study based on interim results at this stage. Other endpoints may be summarised as the data allows. Safety data will also be reviewed and summarised as appropriate.

There will also be an interim analysis (Interim 2) when all participants have had the opportunity to complete D28 procedures (by phone call) to assess the primary endpoints, response rate, time to response, time to discharge and 28-day mortality, as appropriate. These analyses will enable key results to be understood as soon as possible, without compromising the study. In addition, safety will be summarised by incidence of TEAE and SAE by treatment arm. Graphs showing the time course for oxygen levels and 6-point ordinal score and Kaplan-Meier plots for time-to-event variables will be provided.

Final analyses will be carried out after all participants have either discontinued prematurely from or completed the study, by completing the follow-up visit.

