2.2.1.2 Secondary efficacy endpoint(s)

All time to event endpoints are measured from date of randomization. It is expected that there will be approximately 24 hours between randomization and dosing.

All endpoints associated with each secondary objective are listed together. The key endpoints are written in bold to be analysed/summarized at the second interim analysis when all participants have had the opportunity to complete Day 28 Procedures. Collected endpoints and their timing that may be used to derive the endpoints are listed in the third column. Alternative sources of the same information may be available and used.

There is overlap on some of the measurements across endpoints. Some may be taken once for each endpoint or taken once and used for more than one endpoint.

Details of the items in the 6-point ordinal score are provided below this table. Brief details of SOFA, are provided and further information can be obtained from the hyperlink.

Secondary Objective	Endpoint	Measurement

1) To study if early intervention with Zilucoplan® affects clinical outcome defined by duration of hospital stay, 6-point ordinal scale, time to defervescence, supplemental oxygen use, SOFA score
	
Incidents of participants reporting each severity rating in 6-point ordinal scale at D1, D6, D15 and D28
 
Change from baseline in 6-point ordinal scale to Day 6, Day 15 and Day 28 (by phone call) weeks post randomisation
 
Time to at least a 2-point improvement or discharge sustained up to D28 on the 6-point ordinal scale during 28-day assessment period
 
Percentage of participants reporting at least a 2-point improvement sustained to D28 or discharge
 
AUEC/Time using the 6-point score recorded daily – up to D15, D28 and all data recorded
 
Percentage of participants who record a 2-point improvement from baseline or discharge at D6, D15 and D28
 
Percentage of participants not deteriorating according to the ordinal scale by 1 or 2 points on D6, D15 and D28
 
6-point ordinal Scale at D6 and D15 and D28 in relation to D-Dimers and complement C5a levels at baseline
	
6-point ordinal scale measured daily up to discharge, D28 and follow-up
 
Lab values at baseline for D-Dimers and C5a

	
Change from baseline in SOFA score (https://www.mdcalc.com/sequential-organ-failure-assessment-sofa-score) to Day 6, Day 15 (or at discharge, whichever comes first)
	
SOFA score measured at D1, D6 and D15

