3.2 General study level definitions

3.2.1 Analysis time points

3.2.1.1 Relative day

The relative day of an event or assessment will be derived using the date/time of first dose of study treatment as reference. This is the date/time of first dose of Zilucoplan® for participants randomised to Arm A and first dose of IV antibiotic for participants randomised to Arm B.

For the purposes of reporting, there is no relative Day 0. Note that the protocol refers to 'Screening (D0 or D1)'. This is to indicate that it is expected that screening will only take 24 hours and ends at first dose on D1. However, for some participants this is two days (D0 and D1) and for others it is only 1 day (D1) Hence the SAP/TFLs will state 'Day -1' if the day before dosing and 'Day 1' if the day of dosing to ensure differentiation of the days.

Relative days for an event or assessment occurring before the date/time of first dose are calculated as follows and preceded by '-':

$$\text{Relative Day} = \text{Event/Assessment Date/Time} - \text{Date/Time of First Dose}$$

If Time has not been collected for the event/assessment, checks must be made to ensure that any Event/Assessment made on the same day, but PRIOR to first dose, is indicated as this will form part of the calculation to identify baseline values.

The relative day for an event or assessment occurring on or after the first dose to the date of the last dose of study treatment will be calculated as follows:

$$\text{Relative Day} = (\text{Event/Assessment Date} - \text{Date of First Dose}) + 1$$

For events or assessments occurring after the date of the last dose, relative day will be prefixed with ‘+’ in the data listings and will be calculated as follows:

$$\text{Relative Day} = \text{Event/Assessment Date} - \text{Date of Last Dose}$$

Relative day will not be calculated in cases where dates are partial and should be presented as “--” in the relevant data listing.

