3.2.1.2 Study periods

The following are defined as study periods:

Screening	Prior to the time of first dose of Zilucoplan® (Arm A) or IV antibiotic (Arm B)
Primary Assessment Period	For Arm A, from the date/time of first dose of Zilucoplan® to the end date* of the Primary Assessment Period For Arm B, from the date/time of first dose of IV antibiotic to the end date* of the Primary Assessment Period
Planned Active Treatment Duration	For both arms the planned active treatment duration is from D1 up to D14 or hospital discharge, whichever is earlier.
D28 (minimal assessments carried out (6-point ordinal scale, (S)AE supplemental oxygen need (Y/N), concomitant medication)	28 days post randomization (by phone call, unless still hospitalised)
Follow-up	12-22 weeks post randomisation

* The end date of the primary assessment period for each participant will be 28 days post-randomisation

The end of the study is defined by the date of the Follow-up visit for the last participant to complete their Follow-up visit. In the event that participants are lost to follow-up, the study is not deemed to have ended until the last participant dosed has had the opportunity to complete their follow-up visit as scheduled.

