3.2.1.3 Nominal Days

The pre-specified protocol nominal days are labelled as follows:

- Day -1
- D1
- D2

- D6
- D15
- D28
- Follow-up

The study protocol specifies that clinical and laboratory parameters be collected as frequently as possible, which would be daily. A window of +/- 1 relative day for each specified nominal day after D2 (+ 1 day for D2) will be allowed if a measurement was not collected on the specified relative day. The window for D28 is +/- 3 days. If a large proportion of data fall outside this window, then increasing the window to +/-2 days for nominal D6, nominal D15 and D28 will be considered.

An additional indicator variable will be derived, DISCHARGE DAY (Y/N), which will identify the relative day that the participants was discharged from hospital. If discharge is on or earlier than relative day 6, between relative day 7 and relative day 15 inclusive or between relative day 16 and relative day 28 inclusive, an additional row mapping the results of the discharge visit to nominal D6, or nominal D15 and nominal D28 respectively. For the primary endpoints a LOCF approach will be utilized for the participants who discharge i.e. if a participant discharges at Day 4 then that oxygenation measure will be mapped to Day 6, Day 15 and Day 28. The approach may be extended to secondary parameters. Data from participants who leave hospital for reasons other than clinical improvement will not be mapped to the nominal days as described above. Participants who die whilst in hospital are not considered as ‘discharged’. Separate indicator variables will be derived to indicate whether a participant has died on a specific relative day and if treatment was discontinued due to an adverse event.

The Nominal Day variable with the above labels will be derived from the relative days and allowable window for all collected endpoints. Since the ideal is to take measurements as frequently as possible, some measurements of some endpoints will not have a Nominal Day associated with them. When these values (without an associated Nominal Day) are to be summarized, graphed or analysed in statistical models, Relative Day will be used as either a continuous variable or categorical as defined in the respective sections. Nominal Day will only ever be used as a categorical variable.

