10.2 Adverse events

An AE is any untoward medical occurrence in a participant or clinical investigation participant administered a pharmaceutical product that does not necessarily have a causal relationship with this treatment. An AE can therefore be any unfavorable and unintended sign (including an abnormal laboratory finding), symptom, or disease temporally associated with the use of a medicinal (investigational) product, whether or not related to the medicinal (investigational) product.

AEs are further characterised as pre-treatment or treatment emergent.

A pre-treatment AE are events whose onset date and time is prior to the first administration of study drug (Zilucoplan® for Arm A and IV antibiotic for Arm B).

A TEAE is defined as any AE with a start date/time on or after the first dose of study treatment up until the D28 visit. Any AE with an onset date later than the D28 visit for a participant will not be considered as treatment-emergent and therefore will not be included in the tabulations of TEAEs. Where dates are missing or partially missing, AEs will be assumed to be treatment-emergent, unless there is clear evidence to suggest that the AE started prior to the first dose of study treatment. Missing or partially missing dates for AEs will be handled as described in [Section 4.2.3](#). All AEs for a participant will be recorded in the eCRF from the time of informed consent until completion or early study discontinuation.

For each AE the following information should be provided in the eCRF: AE term (verbatim), date and time of onset, whether or not the AE was classified as an SAE, relationship to study treatment, severity, action taken with study treatment, other action taken, outcome, date and time of outcome and whether the AE led to study treatment discontinuation or to study discontinuation.

COVID-19 infection is a very recent syndrome, on which few data are available. Therefore, normal symptoms and natural disease course symptoms that will not be reported as adverse events are dyspnea, coughing, malaise, fever, drop in oxygen saturation, progression to respiratory failure, progression to ARDS, drop in blood pressure. However, progression to multi-organ failure may have other etiologies and will be reported as an SAE.

The number and percentage of participants who experience TEAEs will be summarized by MedDRA preferred term (PT) and treatment.

Summaries of TEAEs may include the following:

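### Day 1 and the start of treatment-emergent events are a different event in each arm, so day-based summaries and TEAE tables can be offset by arm if dosing delays differ

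*SAP*

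**What the plan says.** SAP 3.2.1.1 sets the reference for Relative Day as "first dose of Zilucoplan® for participants randomised to Arm A and first dose of IV antibiotic for participants randomised to Arm B". Three further rules depend on it or repeat it.

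- **Nominal days (SAP 3.2.1.3).** "The Nominal Day variable with the above labels will be derived from the relative days and allowable window for all collected endpoints". D6 and D15 have a window of ±1 day. The discharge bands (up to day 6, days 7–15, days 16–28) are also in relative days.
- **Primary assessment period (SAP 3.2.1.2).** It starts at the arm-specific first dose but ends at a common point: "The end date of the primary assessment period for each participant will be 28 days post-randomisation".
- **Adverse events (SAP 10.2).** A pre-treatment event is one with onset "prior to the first administration of study drug (Zilucoplan® for Arm A and IV antibiotic for Arm B"). Later events, up to the D28 visit, are treatment-emergent.

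On the interval between randomisation and first dose, SAP 2.2.1.2 states "It is expected that there will be approximately 24 hours between randomization and dosing", whereas SAP 2 states "It is assumed that first dose occurs very soon after randomisation". Neither statement is by arm.

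Protocol 5.1 describes the primary comparison as running to "values predose day 6 and to values at day 15 (or discharge whichever comes first) post-randomization in group A and group B". SAP 2.2.1.2 measures time-to-event endpoints from randomisation. Protocol 4.1, however, calls day 1 pretreatment, and Protocol 13.2.1 begins adverse event recording at first drug administration.

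**The concern.** In a randomised comparison, time zero should be the same event in both arms. Randomisation is such an event. So is the first IV antibiotic dose, which both arms receive. The SAP instead lets Arm A's clock wait for Zilucoplan while Arm B's clock starts with the antibiotic.

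If the wait differs by arm, a given study day falls at a different time after randomisation in each arm. Patients discharged equally long after randomisation can also land in different bands. For safety, an event that follows the antibiotic but precedes Zilucoplan is pre-treatment in Arm A, while an event that follows the same antibiotic in Arm B is treatment-emergent. The trial is open-label and has only 27 planned controls, so a by-arm counting rule is best avoided where a common one costs almost nothing.

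**Working it through.** **1. The plan's own figure.** Inputs from Protocol 11.1 and SAP 2.4: 54 and 27 patients, SD 105, difference 80, two-sided 5%.

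- SE = 105 × √(1/54 + 1/27) = 24.75. Power = Φ(80/24.75 − 1.96) = 89.8%.
- With 10% dropout (48.6 and 24.3): SE = 26.09 and power = 86.6%.

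This agrees with the stated figure of more than 85%. The choice of Day 1 changes neither the sample size nor the power.

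**2. Are the two anchors meant to coincide?** Largely, yes. The schedules in both documents put randomisation, first Zilucoplan and the first cephalosporin dose at D1. Protocol 8.1.8 has Arm A's antibiotic run "from the beginning of Zilucoplan[®] administration until 14 days after cessation of Zilucoplan". The offset is therefore (delay to Zilucoplan in Arm A) − (delay to antibiotic in Arm B). Neither term is given, and the offset is zero if they are equal.

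**3. What a one-day offset does.** From first dose to last dose, Relative Day = date − date of first dose + 1. Only calendar dates enter, so a gap within one date moves nothing, but a gap across midnight moves one day. As an assumption, take Arm B dosed on the randomisation date and Arm A one date later.

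| | Arm A | Arm B |
|---|---|---|
| D6, days after randomisation | 6 | 5 |
| D15, days after randomisation | 15 | 14 |
| Discharge 6 days after randomisation | relative day 6, D6 band | relative day 7, D15 band |
| Length of primary assessment period | 27 days | 28 days |

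One day is 1/5 = 20% of D1–D6, 1/14 = 7.1% of D1–D15 and 1/28 = 3.6% of a 28-day adverse event window. A six-hour gap (0.25 day) is 0.9% of that window, and it still matters for TEAEs because SAP 10.2 classifies by date and time.

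**4. Daily endpoints.** The ordinal scale is scored daily, so a shifted clock selects different values. For AUEC/Time to D15, taken approximately as the sum of daily scores over 15, a one-day shift drops one early score and adds one later score. With a dropped score of 2–5 (the hospitalised categories) and an added score of 1–6, one patient's value changes by at most 4/15 = 0.27 points in either direction. The response bands in SAP Table 8.1 (D1–D6, D7–D15, D16–D28) move in the same way as the discharge bands.

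**5. Blood-gas primary endpoint.** SAP 8.1.1 says the eCRF collects PaO2 only at Screening/Day −1, D1, D6 and D15.

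- *Re-anchoring.* In the example, counting from randomisation makes Arm A's pre-dose D6 sample day 7. The ±1 day window returns it to D6 when no day-6 sample exists. Mostly the same values enter the model.
- *Baseline.* Arm A uses the last value before its own first Zilucoplan dose (SAP 3.2.2.1). With a fresh D1 sample, a later dose moves baseline and D6 together, and the interval barely changes. The interval lengthens mainly where a screening sample serves as baseline, which Protocol 7.3 allows if it was taken less than 24 hours before randomisation.

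**6. Illustration only.** Assume drift in PaO2/FiO2 of 2 to 20 mmHg per day, 25% to 100% of one arm offset by a day, and baseline not moving. The shift is drift × fraction = 0.5 to 20 mmHg. The two-sided rejection rate under no effect, P(|Z + shift/24.75| > 1.96), is then 5.0% to 12.8%. Every input to the shift is assumed.

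**The case against.** The strongest reply is that the two anchors are one event in practice. Both are planned for D1, Arm A's antibiotic is tied to the start of Zilucoplan, and the 24-hour sentence is not arm-specific. Giving a day to Arm A and nothing to Arm B has no support in the documents. This stands, and it limits the point to a possible offset.

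The reply continues that re-anchoring would not move blood draws, that mortality at 28 days and the D28 contact already run from randomisation, and that dating treatment emergence from the investigational drug is conventional. The first two stand. The third is fair for describing Arm A alone, but does not justify a different starting event in the arm it is compared with. Nor are early Arm A events lost: SAP 10.2 records events from consent and lists all of them. They are only left out of the TEAE tables.

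A reader might infer that the protocol anchors all days to randomisation and the SAP departs from it. The documents do not support that. Protocol 5.1 uses randomisation, but the same sentence speaks of a predose day 6, Protocol 4.1 refers to pretreatment, and Protocol 13.2.1 starts adverse event recording at first drug administration.

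**Conclusion.** The by-arm definition of Day 1, of the start of the primary assessment period and of the TEAE start is explicit in the SAP and unnecessary. Its effect depends on delays that the documents do not give. It is nil if the delays match. A one-day difference would move discharge and response bands by one day, change a patient's AUEC/Time to D15 by up to about 0.27 points, and put one of 28 days of adverse events under different rules by arm. For TEAEs alone, a gap of hours is enough.

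Two stronger readings are tempting. One is that the rule favours Zilucoplan. That needs a longer delay in Arm A, patients who are recovering, and a baseline that does not move with the dose. The efficacy effect reverses if the antibiotic is the later event or patients are worsening. The other is a definite inflation of type I error. The 5.0% to 12.8% range in the illustration follows from its assumptions and says nothing about this trial. Neither reading is supported. For the blood-gas endpoint any effect is expected to be small, with no derivable size or direction.

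This is a low-cost improvement to the SAP. It does not show that the primary inference is biased.

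**What to change.** 1. In SAP 3.2.1.1–3.2.1.3, set Day 1 to the date of randomisation in both arms for efficacy Relative Day, Nominal Day, response bands and discharge bands. This agrees with Protocol 5.1 and SAP 2.2.1.2. Align the time-to-response row of Table 8.1, which censors on relative day. Keep first-dose dates for exposure, PK and the pre-dose baseline.
2. Start the primary assessment period (SAP 3.2.1.2) from the same point in both arms.
3. In SAP 10.2, start the between-arm TEAE comparison at one common event, either randomisation or the first IV antibiotic dose. Keep a separate Arm A table counted from first Zilucoplan. Reconcile the start of adverse event recording (Protocol 13.2.1: first drug administration; SAP 10.2: consent).
4. Tabulate time from randomisation to first Zilucoplan and to first IV antibiotic, by arm.
5. Reconcile the statements in SAP 2 and SAP 2.2.1.2 on the interval from randomisation to dosing.

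The cost is SAP wording, one changed derivation and one table. No new data are needed, and the sample size and power stay the same. The downsides are minor: a few Arm A events before Zilucoplan would count as treatment-emergent in the common comparison, and some pre-dose samples would fall a day later, within the existing window.

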Data listings containing documented and calculated data (eg, change from Baseline) may be generated if it supports the interpretation of any analysis. Unless otherwise stated, listings will be sorted by treatment arm, participant number within arm, parameter (if applicable), nominal day and relative day respective to first dose and relative day with respect to last dose for any data collected after discontinuation from treatment. All listings will include all measurements which will appear in chronological order together with the scheduled nominal days. In all listings dates will be presented in the format ‘YYYY-MMM-DD’ and times will be presented as ‘hh:mm’ or ‘hh:mm:ss’ as needed.

A listing of reasons for screen fail will be provided for participants who fail screening. A listing of reasons for not being dosed will be provided for participants who were randomized but not dosed. will also be provided.

Appropriate descriptive statistics will be provided in summary tables by treatment and Nominal Day for all endpoints, collected or derived. A total column will always be presented.

Figures will be generated to visualise all the raw data (not just those that fall on the nominal days) to aid interpretation of the results as indicated in their respective sub-sections in Section 8.

Treatment labels for TFLs

Full treatment regimen	Summary tables label	Listings label
Group A: Standard of Care + Zilucoplan 32.4mg i.v. + prophylactic antibiotics	Zilucoplan 32.4mg i.v. + Standard of Care	Group A: Zilucoplan 32.4mg i.v. + Standard of Care + prophylactic antibiotics
Group B: Standard of Care + prophylactic antibiotics	Standard of Care	Group B: Standard of Care + prophylactic antibiotics
Notes:	Standard of Care maybe abbreviated to 'SoC' if so add Footnote: SoC=Standard of Care	Standard of Care maybe abbreviated to 'SoC' if so add Footnote: SoC=Standard of Care If the label is still too long for some listings the 'Group A/B' may be dropped'.

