3.8 Changes to protocol-defined analyses

The analysis of the primary endpoint described in the protocol omitted to add that baseline*day would be included as a fixed effect in the Mixed Model Repeated Measures (MMRM) analysis. This is needed in order to account for the fact that values from days closer to baseline are likely to be more correlated than values at days further apart from baseline. This is important if we include D28 and long-term follow-up in some of our analyses.

The primary analyses will be using Nominal Day as the categorical time point, and not strict relative day. This is because whilst the ideal is to take measurements as frequently as possible, the protocol only specifies specific days, which are the primary days for comparing between treatment arms. Therefore, windowing has been incorporated into the derivation of Nominal Day to ensure data that may not have been collected on the specific day of interest, but are within the window, are used. Sensitivity analyses using Relative Day (continuous and/or categorical) will be carried out as described in the relevant sections.

An additional variable will be created to indicate day of discharge and where needed, the results on the day of discharge will be mapped to the appropriate nominal day (Section 3.2.1.3).. This is to match with the sentence in Section 7.1.2 where it describes how to treat data if the day of discharge is prior to D15.

The SAP will not be amended for any changes to planned analyses or any additional analyses that are made after database lock

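### SAP 3.2.1.1 gives Relative Day two incompatible formulas and 3.2.1.3 does not say which one feeds Nominal Day; taken literally, post-treatment Day 15 blood gases fall outside the D15 window

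*SAP*

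**What the plan says.** SAP 3.2.1.1 opens with a general rule: "The relative day of an event or assessment will be derived using the date/time of first dose of study treatment as reference". For Arm A that dose is Zilucoplan; for Arm B it is the IV antibiotic. The section then splits the calculation. The formula (date − first dose) + 1 is limited to assessments up to the date of the last dose. For later ones the text reads "For events or assessments occurring after the date of the last dose, relative day will be prefixed with" a plus sign in the data listings, and it gives the calculation as assessment date minus date of last dose. Both results carry the same name, Relative Day.

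SAP 3.2.1.3 then states: "The Nominal Day variable with the above labels will be derived from the relative days and allowable window for all collected endpoints". The windows use the same variable: "A window of +/- 1 relative day for each specified nominal day after D2". So does the discharge mapping, which begins "If discharge is on or earlier than relative day 6, between relative day 7 and relative day 15 inclusive" and continues with a third band, "between relative day 16 and relative day 28 inclusive". No sentence there excludes assessments made after the last dose or names the count to be used.

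SAP 3.8 carries this into the main result: "The primary analyses will be using Nominal Day as the categorical time point, and not strict relative day". SAP 8.1.2 fits the MMRM at nominal D6 and D15.

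**The concern.** Day 15 comes after treatment by design, because Zilucoplan is given for at most 14 days (Protocol 8.1.5). The D15 primary assessment of anyone who completes treatment is therefore governed by the formula that restarts at the last dose. The same applies to D6 for anyone who stops early but remains on study, which SAP 4.2 allows.

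If a programmer follows 3.2.1.1 and 3.2.1.3 exactly, one of the two primary timepoints loses most of its in-hospital values. The sensitivity analyses that use Relative Day as a continuous or categorical time variable (SAP 3.8) would also run on a variable that goes backwards: for a full course, study day 15 and study day 1 both carry the number 1. If the programmer uses the first-dose count instead, none of this happens. The plan does not settle which is correct.

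**Working it through.** **Inputs.**
- Formulas: SAP 3.2.1.1.
- Windows: SAP 3.2.1.3, giving D2 = 2–3, D6 = 5–7, D15 = 14–16 and D28 = 25–31.
- Discharge bands: up to 6, 7–15 and 16–28 (SAP 3.2.1.3).
- Arm A last dose: D14 for a full course (Protocol 8.1.5).
- Arm B last dose: not defined. One week of IV antibiotic from D1 (SAP 2) suggests about D7. The planned active treatment duration in SAP 3.2.1.2 suggests D14 for both arms.

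**Plan's own figure.** No stated figure is in dispute here. The power claim of more than 85% (SAP 2.4) reproduces. The standard error is 105 × √(1/54 + 1/27) = 24.75, and 80/24.75 − 1.96 = 1.27, so power is 89.8%. With 10% dropout (48.6 v 24.3) it is 86.6%. The choice of day count does not enter this calculation.

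**Literal application.** Up to the last dose, relative day equals study day. Afterwards it is study day minus the day of the last dose.

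| Case | Last dose | Study day | Relative day as written | Window it meets | Window from first dose |
|---|---|---|---|---|---|
| Arm A, full course | 14 | 14 | 14 | D15 | D15 |
| Arm A, full course | 14 | 15 | 15 − 14 = +1 | none | D15 |
| Arm A, full course | 14 | 16 | 16 − 14 = +2 | D2 | D15 |
| Arm A, stops early, stays on study | 4 | 6 | 6 − 4 = +2 | D2 | D6 |
| Arm B, last antibiotic taken as D7 | 7 | 15 | 15 − 7 = +8 | none | D15 |
| Arm B, last dose taken as D14 | 14 | 15 | 15 − 14 = +1 | none | D15 |
| Arm A, later antibiotics counted as treatment | 28 | 15 | 15 | D15 | D15 |

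**What this does to the primary endpoint.** SAP 8.1.1 says the eCRF takes PaO₂ and PaCO₂ only at Screening/Day −1, D1, D6 and D15, and that the endpoints are calculated from the blood gas form. There is therefore generally no later in-hospital blood gas that could move into the D6 or D15 window. The result is missing D15 values, not values filled in from other days. The exception would be extra blood gases taken beyond the schedule, which 8.1.1 encourages where possible.

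**Discharge mapping.** A participant discharged on the day of the last dose keeps the first-dose count and maps correctly. If the Arm B last dose is D7, discharges on study days 8–13 become +1 to +6 and fall in the D6 band instead of the D15 band. If an Arm A participant's last dose is the day before discharge, the discharge day becomes +1 and also falls in the D6 band. These are the cases in which a scheduled blood gas could be placed on the wrong nominal day.

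**Under the first-dose count.** Study days 14–16 map to D15 and days 25–31 to D28, identically in both arms.

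**The case against.** The strongest reply is that the SAP plainly meant a first-dose count and that the last-dose version is only a display convention. There is good support for this:

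- The opening rule of 3.2.1.1 refers to first dose, and the plus sign is tied to listings.
- SAP 3.1 names two separate counts when describing how listings are sorted: "relative day respective to first dose and relative day with respect to last dose for any data collected after discontinuation from treatment".
- Table 8.1 summarises procalcitonin in seven-day periods counted from the first dose.
- The discharge bands run without a break to 28, which reads naturally only from first dose when dosing ends by D14.
- SAP 3.2.1.2 sets D28 at 28 days after randomisation. On the literal formula a full-course Arm A participant would reach relative day 28 on study day 14 + 28 = 42.

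A near-empty D15 would also be noticed as soon as the analysis was run, at the latest at Interim 1, so it would not be a hidden bias.

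This stands as evidence of intent, and it rules out treating misassignment as certain. It does not remove the problem. The sentence in 3.2.1.1 sets the calculation as well as the prefix, the first-dose formula is expressly limited to the period up to the last dose, and 3.2.1.3 lacks the first-dose wording that Table 8.1 uses. In an open-label trial the allocation of data to primary timepoints should not wait until someone sees that the output looks wrong.

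**Conclusion.** The SAP contradicts itself on the time variable of its primary analysis. Read literally, a full-course Arm A participant's Day 15 blood gas is numbered +1 and leaves the D15 window, and a D4 stopper's Day 6 value is numbered +2 and leaves the D6 window. The main consequence would be missing D15 values, and some missing D6 values, among participants still in hospital. Arm A values taken on Day 14 and discharges on the last-dose day are unaffected.

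A reader might infer that D15 is bound to be misclassified, or that the error necessarily differs between arms. The documents support neither. The text cited under the objection points to a first-dose count. The arm difference rests on a last-dose date that the SAP does not give for Arm B: with an antibiotic end at about D7, Day 15 is +8 in Arm B against +1 in Arm A; with D14, it is +1 in both. If Arm A's later antibiotics counted as study treatment, as SAP 7 could be read, its Day 15 would stay at 15, although 3.2.1.1 ties the Arm A first dose to Zilucoplan. Nor would the primary D15 cell generally be filled with later values, given the blood gas schedule.

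The point needs settling because it governs a primary timepoint, but it is a drafting contradiction with a clear probable intent.

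**What to change.** In SAP 3.2.1.1, define Relative Day as (date − date of first dose) + 1 for every on-study assessment from first dose onwards in both arms, including those after the last dose. In 3.2.1.3, state that Nominal Day, the windows and the discharge mapping use only this variable. Say the same for the efficacy day bands in Table 8.1 and for any model that uses Relative Day.

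Keep days since last dose as a separately named variable for listings only, and define the Arm B last-dose date on which it depends, reconciling 3.2.1.1 with 3.2.1.2.

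The cost is a few sentences and one renamed variable, to be settled before database lock. No new data are needed, the sample size and power are unchanged, and there is no analytical downside.
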